E-cigarette use appears to be growing and highest among young adults 18-24 years. A study conducted in Hawaii found that smokers who used e-cigarettes to try to quit were younger and had been smoking for fewer years than those who had not. Notably, the most recent analysis of trends in smoking in the US found that between 2005-2010 young adults had the lowest quit rates compared to other adult age groups (CDC 2014). These findings suggest a rationale for focusing on the young adult population in studying the potential use of e-cigarettes as a harm reduction strategy. There are an estimated 2.5 million e-cigarette users in the US with sales of \$300 million a year (McCauley 2012). Many of these users are turning to e-cigarettes as a way to reduce or stop smoking. More research is needed to assess the effect of e-cigarette use on withdrawal symptoms, and its association with smoking reduction and abstinence.

The rationale for this harm reduction pilot study is based upon prior work demonstrating that pre-cessation nicotine replacement therapy (NRT) has been shown to increase the odds of reducing consumption of cigarettes per day (CPD by 50% or more compared to placebo) (Stead 2010). This prior work is especially noteworthy because smokers not interested in quitting made significant reductions in their smoking and maintained these reductions over time. Concern that pre-cessation NRT use will result in fewer quit attempts and impede cessation has not been supported by the literature. Among 19 relevant studies, none showed that pre-cessation NRT undermined future cessation. On the contrary it

Name of study: Assessing the use of electronic cigarettes (e-cigarettes) as a harm reduction strategy

appears that pre-cessation NRT is associated with smoking reduction which in turn increases the probability of future cessation (Hughes 2006).

METHODS

Primary research questions:

- 1) Is it feasible to recruit and retain young adult smokers in a pilot trial testing whether e-cigarette use can reduce the number of cigarettes smoked per day (CPD)?
- 2) To what extent do smokers reduce CPD when using e-cigarettes to displace cigarette use?
- 3) Are there differences in rates of reduction between two interventions arms (4.5% vs. 0 mg (placebo) e-cigarettes)?

Study Aims

AIM 1: To evaluate the feasibility of recruiting and retaining young adult smokers in a harm reduction study using e-cigarettes to displace cigarette use;

[figure not shown]

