AIM 2: To assess daily patterns of e-cigarette use (including dual use of combustible cigarettes), product satisfaction, and nicotine cravings with use of 4.5% vs 0 mg (placebo) e-cigarette; and

AIM 3: To compare the effect of nicotine e-cigarettes (4.5%) vs placebo e-cigarettes on smoking reduction at 1, 3 and 12 weeks post baseline assessment.

Study design

This pilot study will be a two-arm, randomized controlled trial. We will randomize 50 participants into each intervention arm. Participants will be recruited through advertisements placed in Craigslist and other social media as well as flyers placement in NYU venues and street distribution with contact details for how to get in touch with a Research Assistant. The randomization sequence will be prepared by the study statistician. Participants will be randomized to one of the two arms: e-cigarettes with nicotine cartridges or e-cigarettes with placebo cartridges (0mg). Participants and research assistants will be blind to the allocation of nicotine or placebo e-cigarettes as there are no difference in appearance or odor of the mist emitted from the e-cigarettes with and without nicotine containing cartridges.

Figure 1. Study design

Study participants

Inclusion criteria: ages 21-35 (must present proof of age), daily smoker, smokes at least 10 cigarettes a day (verified by a CO level of 8 ppm or above), interested in reducing CPDs, able to provide consent, uses a cell phone and is willing/ able to receive and respond to daily text messages regarding his/her cigarette use and e-cigarette use on his/her cell phone, and willing to use an e-cigarette for 3 weeks.

Exclusion criteria: Pregnant and/or breastfeeding (self-reported), current use of smoking cessation medications (including other forms of NRT, bupropion, or varenicline), enrolled in a smoking cessation program or another cessation trial. Other exclusion criteria include use of an e-cigarette in the past 14 days, use of any other tobacco products (pipe, cigar, cigarillos, snuff, chewing tobacco, or hookah/shisha) in the past 30 days, an Alcohol Use Disorders Identification Test (AUDIT C) score of ≥ 7

Name of study: Assessing the use of electronic cigarettes (e-cigarettes) as a harm reduction strategy

for men and ≥ 5 for women, a Drug Abuse Screening Test-10 (DAST) score of ≥ 5 . Potential participants will also be excluded if they report having a history of asthma or other airways disease and heart disease.

Study Procedures

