Table 2. Text messages and schedule

Rule (based on answer to the first question)	Text	3 days baseline tracking cig use				Intervention period			
		1 st	2 nd	3 rd	4 th	1 st	2 nd	3 rd	4 th
	Since your last report: Did you smoke a cigarette and/or E-cigarette? [no=0; cig=1; Ecig=2; both=3]	X	X	X	X	X	X	X	X
	Thinking about this morning, how many minutes after waking did you smoke your first cigarette? (Text 9999 if you did not smoke any cigarettes today)				X				X
	Thinking about this morning, how many minutes after waking did you use your first E-cig? (Text 9999 if you did not use any E-cigs today)								X
	Thinking about TODAY only: Do you want to smoke fewer cigarettes than usual? [0=Not at all ; 9=Very, Very Much]					X			
	Thinking about TODAY only: How hard would it be to use E-cigs ONLY? [0=Not at all ; 9=Extremely]					X			
If used cig	Since your last report: How many cigarettes did you smoked?	X	X	X	X	X	X	X	X
If used cig	How many minutes ago did you smoke a cigarette? [Text "0" if your are currently smoking]	X	X	X	X	X	X	X	X
If used cig only	On a scale of 0-9 how satisfying was your last cigarette? [0=Not at all – 9=Extremely Satisfying]	X	X	X	X	X	X	X	X
If used e-cig	Since your last report: How many separate times did you use an E-cigarette?					X	X	X	X
If used e-cig only	On average, how many puffs did you take with each use?					X	X	X	X
If used e-cig	How many minutes ago was your last E-cigarette puff? [Text "0" if you are currently using an E-cigarette]					X	X	X	X
If used e-cig	On a scale of 0-9 how satisfying was your last E-cigarette? [0=Not at all – 9=Extremely Satisfying]					X	X	X	X
	On a scale of 0-9, how much do you want to smoke a CIGARETTE right now? [0=Not at all – 9=Very, Very much]	X	X	X	X	X	X	X	X
	Thank you for completing the survey.	X	X	X	X	X	X	X	X

Primary outcome: For Aim 3, the primary outcome will be reduction in CPD and we will summarize this data as the proportion of participants who achieve 50% reduction in CPD at 3 weeks. Smoking reduction will be measured by a combination of self-report, text message data and changes in CO and saliva cotinine between baseline and end of treatment (3 weeks).

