Secondary outcomes: We will assess potential side effects associated with e-cigarette use, additional use of other tobacco products and/or marijuana, satisfaction with the e-cigarettes, nicotine urges/cravings and withdrawal symptoms. An exploratory secondary aim includes assessing differences in the primary and secondary outcomes between the intervention arms.

Name of study: Assessing the use of electronic cigarettes (e-cigarettes) as a harm reduction strategy

Feasibility measures include: 1) Percentage of subjects screened who are eligible and enroll, 2) percentage retained at 3 and 12 weeks, 3) retention across study conditions, 4) consistency in tracking use of e-cigarettes and cigarettes, and 5) satisfaction with e-cigarettes.

Characteristics of the Research Population

Described above under the study participants section.

Number of Subjects

We expect to enroll 100 smokers total, 50 in each arm.

Gender of Subjects

We would ensure equitable inclusion of both men and women in this study.

Age of Subjects

All subjects will be 21-35. We are particularly interested in studying the effectiveness of e-cigarettes as a harm reduction strategy among young adults as this is an understudied population and one that has demonstrated exceptionally high rates of adoption of this product.

Racial and Ethnic Origin

We will recruit across all racial and ethnic groups.

Inclusion Criteria

All subjects must be between 21-35 years old, daily smokers, smoke at least 10 cigarettes per day, interested in reducing CPDs, able to provide consent, use a cell phone, are willing/able to receive and respond to daily text messages regarding their cigarette use and e-cigarette use on their cell phone, and are willing to use an e-cigarette for 3 weeks.

Exclusion Criteria

Subjects will be excluded if they are pregnant and/or breast feeding (self-reported), are currently using smoking cessation medications (including other forms of NRT, bupropion, or varenicline), are enrolled in a smoking cessation program or another cessation trial, have used an e-cigarette in the past 14 days, have used any other tobacco products (pipe, cigar, cigarillos, snuff, chewing tobacco, rolling tobacco, or hookah/shisha) in the past 30 days, score ≥ 7 (men) or ≥ 5 (women) on the Alcohol Use Disorders Identification Test (AUDIT-C), score ≥ 5 on the Drug Abuse Screening Test-10 (DAST), or report having a history of asthma, other airways diseases, or heart disease.

Data Analysis and Data Monitoring

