
All measures collected during study visits and by telephone at 12 weeks, will be summarized for each time point with standard descriptive statistics and frequency tables, as appropriate. Measures with significant baseline treatment group differences (assessed by analysis of variance or chi-squared as appropriate to the primary outcome measure) will be considered for inclusion as covariates in a generalized linear mixed model analysis.

In terms of the EMA data, as per Shiffman (2013), analysis of the EMA data will be handled through several different approaches depending on the research question. For example, if we want to assess differences between individuals with no reference to change over time we can ask if there is a correlation between cravings and e-cigarette use. Data would be collapsed over time, averaging craving ratings for each subject from all signal-contingent assessments in order to derive a single

Name of study: Assessing the use of electronic cigarettes (e-cigarettes) as a harm reduction strategy

craving score. Using simple Pearson correlation across subjects we can assess correlations between cravings and e-cigarette use. If we are interested in assessing how craving intensity changes with changes in cigarette use we would use a GEE model (Shiffman 2013).

We will assess multiple aspects of intervention feasibility including the eligibility rate (the proportion of smokers who were eligible for trial participation), the acceptance rate (the percentage of eligible individuals we recruited to the study) and reasons for study ineligibility and refusal. We will compare retention rates in the two study arms at each study visit (weeks 1,3, and 12). We will also assess consistency in tracking use of e-cigarettes and cigarettes, and satisfaction with e-cigarettes (see measures section). We will compute frequencies and percentages for categorical outcomes and means, standard deviations, medians, and interquartile range for continuous outcomes. As part of our feasibility analysis, we will conduct qualitative interviews with 10 subjects in each arm at 1 and 3 weeks. Interview transcripts will be analyzed with Atlas.ti. A coding manual of core and secondary codes will be developed by [name] and [name], both experienced qualitative researchers. Intercoder reliability will be assessed by examining rates of disagreement.

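### The nicotine-versus-placebo comparison of smoking reduction is both primary and exploratory, and its week-3 contrast and source of cigarettes per day are not fixed

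*Combined protocol and SAP*

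**What the plan says.** The status of the arm comparison is described in four places.

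- Primary research questions, question 3: "Are there differences in rates of reduction between two interventions arms".
- Study Aims, Aim 3: "To compare the effect of nicotine e-cigarettes (4.5%) vs placebo e-cigarettes on smoking reduction at 1, 3 and 12 weeks".
- Primary outcome: "For Aim 3, the primary outcome will be reduction in CPD and we will summarize this data as the proportion of participants" who reach a 50% reduction at 3 weeks.
- Secondary outcomes: "An exploratory secondary aim includes assessing differences in the primary and secondary outcomes between the intervention arms".

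The setting is a pilot: "This pilot study will be a two-arm, randomized controlled trial". On size, Number of Subjects says only "We expect to enroll 100 smokers total, 50 in each arm", with no derivation.

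On measurement, the Primary outcome paragraph says: "Smoking reduction will be measured by a combination of self-report, text message data and changes in CO and saliva cotinine". The changes are taken from baseline to week 3. The baseline survey asks for cigarettes per day. Separately, participants report cigarettes by text for three days before starting to reduce, and then for 21 intervention days.

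On analysis, Data Analysis and Data Monitoring plans descriptive summaries at each time point. It screens measures for baseline differences between treatment groups, with the test chosen to suit the primary outcome measure. Measures that differ "will be considered for inclusion as covariates in a generalized linear mixed model analysis". The arm comparison it states outright is of retention.

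**The concern.** A comparison cannot be both a primary question and an exploratory aim. If the label stays open until the data are seen, the same estimate could be reported as the answer to a primary question or as a hypothesis for a later trial, and a reader could not tell which was intended.

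The second part concerns the endpoint. A fixed 50% cut-off turns a count into a yes or no, so the result depends on which count forms the numerator and which the denominator. Four sources are named with no rule for combining or ranking them, and two baseline values will exist for each participant. One of the four, cotinine, is a marker of nicotine whatever its origin. In the nicotine arm it also reflects the e-cigarette, so a responder rule that used it could count against that arm for reasons unrelated to smoking.

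**Working it through.** The plan gives no power, significance level, response rate or loss rate, so there is no figure to reproduce. The check is mainly a comparison of sections.

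**1. Status.** Question 3 is primary by its heading. Aim 3 is the same comparison, and the Primary outcome paragraph assigns the primary outcome to Aim 3. The Secondary outcomes sentence covers arm differences in the primary as well as the secondary outcomes, so it cannot be confined to the secondary ones. The two descriptions concern the same comparison of the same outcome.

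**2. What the analysis section fixes.** It refers to treatment groups, to the primary outcome measure and to a mixed model, which together imply an arm comparison. It does not give the time point, the effect measure, the CPD derivation or the handling of missing values. Aim 3 and the Primary outcome paragraph together imply the contrast (the week-3 arm difference in the proportion reaching 50%), but the analysis section does not state it.

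**3. Can the source change responder status?** Reduction = 1 − (week-3 CPD / baseline CPD). Take a week-3 CPD of 10 and a survey baseline of 20, and assume that the text baseline is lower by 10%, 20% or 30%:

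- baseline 20: 1 − 10/20 = 50%, a responder
- baseline 18: 1 − 10/18 = 44.4%, not a responder
- baseline 16: 1 − 10/16 = 37.5%, not a responder
- baseline 14: 1 − 10/14 = 28.6%, not a responder

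The labels can be swapped. With a text baseline of 20 and a survey baseline of 18, the texts give the responder. The documents do not say which source runs lower.

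**4. Why one source at both time points helps.** If texts miss the same 10% of cigarettes at baseline and at week 3, the counts are 18 and 9, and 1 − 9/18 = 50% again. A constant proportional error cancels within one source. It does not cancel when sources are mixed.

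**5. Where each source exists.** Texts run for 3 + 21 = 24 days and then stop. Week 12 is a telephone survey, so a text-based definition can serve week 3 but not the week-12 part of Aim 3.

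**6. Precision, as context only.** The only input from the plan is 50 per arm. Equal responder rates p of 20% to 50%, and a reduced 40 per arm (20% loss), are assumptions. The 95% half-width for the arm difference is 1.96 × √(2p(1 − p)/n).

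- n = 50: p = 0.2 gives 1.96 × √(0.32/50) = 15.7 points; p = 0.5 gives 1.96 × √(0.50/50) = 19.6 points
- n = 40: p = 0.2 gives 17.5 points; p = 0.5 gives 21.9 points

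**The case against.** The strongest defence is that a primary outcome names a measure, while the Secondary outcomes sentence gives the status of comparing it between arms. Question 2 asks how far smokers reduce CPD and can use that measure without an arm contrast. A primary outcome with an exploratory comparison is coherent in a pilot. This much stands: the exploratory label is already in the text and is a sensible one. It does not remove the conflict, because question 3 sits under the primary heading and the primary outcome is tied to Aim 3 by name.

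A reader might infer that the analysis section has no arm comparison, or that the mixed model has no link to the primary outcome. That goes too far. The covariate-screening sentence mentions both treatment groups and the primary outcome measure. The gap is in what it leaves unstated.

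A reader might also infer from Table 1, which words the survey item per day on days smoked, that survey CPD is invalid. The documents do not support that. Entrants must be daily smokers, so the wording matters only at follow-up. Table 1 is a schedule rather than the questionnaire, and the follow-up text also lists reduction in cigarettes per day among the week-1 and week-3 assessments.

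Finally, the source example starts exactly at the threshold. That objection is fair and limits what the example shows.

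**Conclusion.** The point holds. The documents give one comparison two statuses, and this rests on their text alone, without any assumption. They also leave the week-3 contrast, effect measure and CPD derivation unstated, so responder status can depend on a choice made later.

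The size of the second effect is unknown. The example shows that a responder can become a non-responder when the baseline differs by 10%. It does not show how often survey and text baselines differ, or in which direction.

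A reader might take the half-widths of about 16 to 20 points as proof that the trial is too small. They rest on assumed rates and do not bear on the labelling conflict. At most, they agree with treating the comparison as exploratory. The trial can run as planned; what is undefined is what its arm comparison may be used to claim.

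**What to change.** 1. Use one status in Primary research questions, Study Aims, Primary outcome and Secondary outcomes. Any single status removes the contradiction. Exploratory is already stated once and suits a pilot with no stated power: report the estimate with a 95% confidence interval and make no efficacy claim from it.
2. In Data Analysis and Data Monitoring, state the contrast as the week-3 arm difference in the proportion with at least a 50% reduction in CPD, using the same source at baseline and week 3. For example, compare mean text-reported CPD over the three tracking days with the mean over a pre-specified window at the end of the 21 intervention days. State how missing texts and participants lost to follow-up are counted.
3. Base the week-12 comparison on survey CPD at baseline and week 12, expressed as average cigarettes per day.
4. Report CO and cotinine changes alongside, outside the responder definition. Week-3 CPD adjusted for baseline CPD from the same source may be added as a supporting analysis.

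The cost is some wording and a little extra analysis. With exploratory status, the sponsor also gives up presenting the comparison as a primary efficacy result. The 50% reduction summary stays the lead.

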1 of ecig use, they will be asked to return to replenish the e-cigarettes for another 2 weeks and to complete a second in-person assessment. The final study visit will be 3 weeks post starting e-cigarettes. We will conduct in depth interviews with a random sample of 10 participants in each intervention arm at the week 1 and 3 study visits. The first visit will focus on a process evaluation of the data collection experience and satisfaction with e-cigarette use while Week 3 interviews will focus on gaining more in-depth understanding of their experience (ease of use, satisfaction) with the product over time, e-cigarette related outcome expectancies and norms and explore intentions to quit and/or continuing dual use of cigarettes and e-cigarettes.

Figure 2. Assessments and intervention period**Data collection and Measures**

Baseline assessments: *Demographic information:* age, race/ethnicity, gender, years of education, employment, income; *Smoking history:* number of cigarettes smoked per day, number of years as regular smoker; use of other tobacco products or e-cigarettes, number of previous attempts in the past 12 months; *Other smoking related information:* self-rated importance and confidence to reduce and to quit, intention/readiness to quit using the readiness ladder, risk perceptions about e-cigarettes and combustible cigarettes, social norms related to using cigarettes and e-cigarettes, an assessment of urges to smoke using the QSU-Brief survey, other household members smoking at home; and the *Behavioral factors in smoking dependence scale* (Glover 2005). We will also measure carbon monoxide and collect saliva for cotinine measurement at baseline and study visit 3.

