Follow-up assessment study visits: At 1 and 3 weeks, we will assess withdrawal symptoms using the Minnesota Nicotine Withdrawal Scale (MNWS), e-cigarette use, cigarette use, quit attempts, and reduction in number of cigarettes used/day. Using Atkinson's treatment satisfaction scale, we will assess side effects associated with using the e-cigarette, convenience of use, perceived effectiveness, and global satisfaction with the product (Atkinson 2004). At the final study visit (week 3) we will also assess changes in baseline readiness to quit, intention to quit, norms related to smoking and using e-cigarettes, confidence in quitting and changes in intention to quit. At 12 weeks post starting e-cigarettes we will conduct follow up telephone surveys to assess current e-cigarette and cigarette use.

At each follow up assessment, RAs will complete a checklist for all of the activities including, completing surveys, and providing e-cigarettes. Note that we will schedule visits up to 4 times. If the subject misses all of those visits he/she will be considered lost to follow up. We will also attempt to contact subjects up to 10 times at different hours of the day and via text message to schedule or reschedule appointment to increase retention rates.

Table 1. In person survey assessments

Measures	Screener	Baseline	Wk 1	Wk 3	Wk 12 telephone
Socio demographics	X				
Smoking history and nicotine dependence		X			
Other tobacco products and marijuana use		X			
Readiness to quit		X		X	

Name of study: Assessing the use of electronic cigarettes (e-cigarettes) as a harm reduction strategy

Importance and confidence in quitting		X	X	
Smoking urges for traditional cigarettes (QSU-Brief)		X	X	
Self-efficacy questionnaire (SEQ12)		X	X	
Secondhand home policy and other smokers at home		X	X	
Risk perception (e-cigarettes)		X		
Social norms		X	X	
History of E-cigarette use		X	X	
Health status		X		
Behavioral dependence scale		X	X	
Current E-cigarettes use		X		
Treatment satisfaction scale (Side effects, Effectiveness, convenience related to e-cigarettes)			X	X
Minnesota Nicotine Withdrawal Scale			X	X
Current cigarette use		X	X	X
1. Someday, every day, not at all				
2. Number per day on days smoke (Self-report and CO and saliva validated abstinence)				
Quit attempt (24 hour) in past week			X	X
Acceptability and Receptivity to txt messages			X	X

Text message assessment:

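### Covariates are chosen by testing the randomised arms for baseline differences; baseline cigarettes per day should be a fixed covariate instead (minor, no cost)

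*Combined protocol and SAP*

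**What the plan says.** The covariate rule is one sentence in Data Analysis and Data Monitoring. "Measures with significant baseline treatment group differences", tested by analysis of variance or chi-squared, "will be considered for inclusion as covariates in a generalized linear mixed model analysis". No significance level is given, the terms of the model are not listed, and no section names a covariate that will always be included.

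The sentence names no aim. It does refer to the primary outcome measure, which the Primary outcome paragraph ties to the third aim in these words: "the primary outcome will be reduction in CPD and we will summarize this data as the proportion of participants who achieve 50% reduction", assessed at 3 weeks. Aim 3 itself asks whether the nicotine and placebo devices differ in smoking reduction at weeks 1, 3 and 12. The Secondary outcomes paragraph puts the comparison lower: "An exploratory secondary aim includes assessing differences in the primary and secondary outcomes between the intervention arms".

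Baseline CPD is collected twice. The baseline survey asks for "number of cigarettes smoked per day, number of years as regular smoker", and three days of text-message tracking follow (Text message assessment). After baseline, the week 1 and week 3 visits record "cigarette use, quit attempts, and reduction in number of cigarettes used/day". At week 12 "we will conduct follow up telephone surveys to assess current e-cigarette and cigarette use". Text messaging lasts 24 days in total and so does not reach week 12.

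**The concern.** Randomisation makes the expected baseline difference zero for every measure. A significant difference is therefore a chance event, and it says nothing about whether the measure predicts the outcome. A covariate earns its place by predicting the outcome, and the natural candidate for an outcome built on CPD is baseline CPD. Under the written rule it enters only by accident, and even then it is merely considered.

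Two things are at stake: precision that data already in hand could supply, and a model settled before the arms are compared.

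**Working it through.** **Inputs.** From the documents: two randomised arms, 50 per arm (Study design; Number of Subjects). The documents give no test level, effect size, SD, correlation or response rate, so there is no stated figure to reproduce. The following are assumptions: two-sided 0.05 for all tests, no attrition, normal CPD with equal SDs at baseline and follow-up, effect 0.5 SD, and baseline-outcome correlation r of 0.3, 0.5 or 0.7.

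**1. How often the rule selects baseline CPD.** Under randomisation the selection probability equals the test level. At 0.05 it is 5%, so CPD is left out in 95% of trials. At 0.01 to 0.20 it is left out in 99% to 80%. Across K independent baseline measures, the chance that at least one is flagged is 1 − 0.95^K: 0.40, 0.51 and 0.64 for K = 10, 14 and 20.

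**2. The stated summary: proportion with 50% reduction.** 20,000 simulated trials per setting, logistic model, by strength of association between baseline CPD and response (odds ratio per SD):

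| Odds ratio per SD | 30% vs 50%: power, rule / fixed | 20% vs 40%: power, rule / fixed | SE of log odds ratio, adjusted ÷ unadjusted (30% vs 50%) | SD of standardised ÷ raw difference in proportions (30% vs 50%) |
|---|---|---|---|---|
| 1 | 0.539 / 0.532 | 0.571 / 0.582 | 1.012 | 1.004 |
| 1.5 | 0.541 / 0.545 | 0.581 / 0.608 | 1.034 | 0.987 |
| 2 | 0.546 / 0.569 | 0.572 / 0.616 | 1.074 | 0.957 |
| 3 | 0.546 / 0.614 | 0.584 / 0.669 | 1.155 | 0.904 |

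The gain is about nil to 3 points up to an odds ratio of 1.5, 2 to 4 points at 2, and 7 to 9 points at 3. The confidence interval for the log odds ratio widens, because the adjusted odds ratio is a conditional one. A difference in proportions standardised over baseline CPD becomes modestly more precise.

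**3. CPD as a continuous outcome.** In SD² units the variance per participant is 2(1 − r) for change, 1 for follow-up alone, and 1 − r² for follow-up adjusted for baseline. The 95% half-width is about 1.984 × √(2/50 × variance). At r = 0.5 this is 1.984 × √(0.04 × 1) = 0.40 for change or follow-up, and 1.984 × √(0.04 × 0.75) = 0.34 adjusted. Power from 40,000 simulated trials per setting:

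| r | Rule, default change | Rule, default follow-up | Always adjusted |
|---|---|---|---|
| 0.3 | 0.564 | 0.700 | 0.734 |
| 0.5 | 0.707 | 0.707 | 0.814 |
| 0.7 | 0.897 | 0.718 | 0.932 |

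The loss is 17, 11 and 4 points with a change default, and 3, 11 and 21 points with a follow-up default.

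The named mixed model could instead carry baseline CPD as a repeated measurement. With one baseline mean common to both arms, power is 0.730, 0.808 and 0.932, so the loss is nil. With separate baseline means per arm it is 0.547, 0.694 and 0.890, close to the change default.

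**4. Type I error.** With one covariate entered mechanically, the rule gives 3.4% to 4.7% for continuous CPD and 4.2% to 4.5% for the proportion (null rate 30%). With 10 or 14 independent measures, each correlated 0.2 with the outcome (8,000 null trials), entering every flagged measure gives 4.6% and 3.6%. Choosing the most favourable flagged subset gives about 6.2% to 6.3%. The simulation standard error there is √(0.05 × 0.95 / 8,000) = 0.24 percentage points, so the excess over 5% is real.

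**The case against.** The strongest reply is that little depends on this. The trial is a pilot with no stated power, and the arm comparison is called exploratory. The primary outcome is summarised as a proportion whose denominator already is baseline CPD. This stands, and it is why the point is minor. A reader might infer from the continuous-outcome figures that the trial forfeits 20 points of power on its primary summary. The documents do not support that: those figures concern a different scale and a default model that the plan never states.

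A second reply is that naming a mixed model may bring baseline CPD in as a repeated measurement. It may, and with a common baseline mean nothing is lost. But the terms are not written down, so the plan does not secure this.

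A third is that equal SDs are doubtful, since entrants smoke at least 10 a day and are encouraged to halve that. The objection is fair, but it does not rescue a change default. With a follow-up SD 0.6 times baseline and r = 0.5, the variance of change is 1 + 0.36 − 0.60 = 0.76 against 0.36 × 0.75 = 0.27 adjusted. That is a ratio of 2.8, compared with 1/0.75 = 1.3 under equal SDs. Attrition was not varied. It would lower all the powers, so the absolute figures are illustrative.

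A reader might also infer that the rule biases the comparison or inflates false positives. Applied mechanically it is slightly conservative. The excess to about 6% arises only if the analyst exploits the freedom that the wording leaves.

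**Conclusion.** The concern holds as a minor point and a free improvement. The rule selects covariates on a criterion unrelated to prognosis, leaves the final choice open, and does not assure a place for baseline CPD. That the sentence governs Aim 3 is an inference from its reference to the primary outcome measure, though a reasonable one.

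For the stated summary, the benefit of fixed adjustment is small unless baseline CPD strongly predicts response. For continuous CPD the loss under the listed assumptions lies anywhere from nil to about 20 points. That width reflects an unspecified model rather than a demonstrated loss. The claim that baseline CPD will certainly be absent from the analysis would go too far, because the plan leaves this open.

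**What to change.** Amend the sentence rather than delete it, because it holds the plan's only mention of the generalized linear mixed model, which other outcomes may also need. Suggested wording:

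> *Between-arm comparisons will use a generalized linear mixed model. For CPD, the response will be the follow-up values only (weeks 1, 3 and 12), with baseline CPD as a fixed covariate whatever the baseline difference between arms. No covariate will be chosen by testing baseline differences.*

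Restricting the response to follow-up values prevents baseline CPD from being both response and covariate.

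Add one line matching sources: survey baseline CPD for self-reported CPD at weeks 1, 3 and 12, and the three-day text baseline only for text-based CPD up to week 3.

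Keep the 50%-reduction proportion at 3 weeks as the stated summary. If it is modelled, use the same covariate, label the odds ratio as conditional, and report the difference in proportions standardised over baseline CPD. How self-report, text, CO and cotinine are combined into the outcome is a separate matter that this change does not settle.

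Cost: one sentence amended and a few lines added, with no new data, visits or participants.
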